5.5 Rationale for this study

To date NT-814 has been tested in 90 volunteers in 4 phase 1 studies of which 15 subjects were dosed with 200 mg up to 29 days. To date only 1 female subject has been dosed. The aim of this study is to investigate the PK and safety of NT-814 in post-menopausal women with hot flashes to help inform design of subsequent studies in the target population. The target population of post-menopausal women is required to have a minimum hot flash frequency and severity requirement for entry into this study. These characteristics have been selected as it is deemed to be important to define the safety profile of NT-814 in a controlled setting in a population with similar characteristics to that to be studied in further development due to the nature of the symptoms associated with the disease under study: hot flashes are often associated with symptoms such as palpitations, tachycardias and dizziness. To help in this assessment a careful pre-dose characterization of the subjects will be carried out on before dosing on Day -1, the study will be placebo controlled and involve 24-hour ECG monitoring through the first 7 days of dosing, when steady state plasma drug levels are predicted to be reached.

This study will be conducted in compliance with the protocol, Good Clinical Practice (GCP), the Declaration of Helsinki (with amendments), and in accordance with local legal and regulatory requirements.

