11.3.3 Pharmacokinetic analysis methodology

Plasma concentration versus time data for NT-814 will be evaluated by standard non-compartmental analysis using appropriate software. Individual plasma concentration versus time profiles for each subject and mean and median plasma concentration versus time profiles by dose will be generated. The following PK parameters will be log-transformed prior to statistical analysis: AUC_{0-t} , $AUC_{0-\tau}$, $AUC_{0-\infty}$, C_{max} , CL/F , and $t_{1/2}$.

For each of the parameters the following summary statistics will be calculated and tabulated by treatment: n, arithmetic mean, 95% CI (confidence interval) for the arithmetic mean, standard deviation, minimum, median, maximum, geometric mean, 95% CI for the geometric mean, and standard deviation of log-transformed data. Between-subject coefficient of variation (%CVb) will also be calculated.

For t_{max} , t_{lag} , n, median, minimum, maximum, arithmetic mean, 95% CI for the arithmetic means and standard deviation will be calculated.

Accumulation and time invariance will be evaluated by comparisons of Day 1 AUC_{0-24} versus Days 7 and 14 and Day 1 $AUC_{0-\infty}$ versus AUC_{0-24} Days 7 and 14 respectively.

Dose proportionality will be assessed on Day 7 (AUC_{0-24} and C_{max}).

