4.9 Pharmacokinetic Sampling Schedule

Blood samples for PK analysis will be collected at the following time points on Days 1, 7, and 14: predose, and 0.5, 1.0, 1.5, 2.0, 2.5, 3.0, 4.0, 5.0, 6.0, 8.0, 12.0, and 24.0 hours postdose. For Cohorts 3 onwards, additional samples will be collected at 48.0 and 72.0 hours after the Day 14 dose.

The predose sample will be collected within 30 minutes prior to dose administration.

Pharmacokinetic samples will be collected as close to the nominal time point as possible. Allowable windows for PK sample collection relative to dosing will be as follows: ± 2 minutes through 2 hours postdose, ± 5 minutes through 8 hours postdose, ± 10 minutes through 24 hours postdose and ± 30 minutes for the 48 and 72 hour postdose samples.

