4.10.5 Electrocardiograms

On Days 1 and 14, resting 12-lead ECG data will be collected at the following timepoints: predose and at 0.5, 1.0, 1.5, 2.0, 2.5, 3.0, 4.0, 8.0, 12.0 and 24.0 hours (all +/- 15 mins).

The same assessment schedule is also required on Day -1, starting at a time similar to that planned for Days 1 and 14. The Day -1 and Day 1, 24 hour ECGs must be performed prior to the dose of study medication the following morning (on Days 1 and 2, respectively).

Once-daily ECG recordings will be just prior to dosing (approx. 30 mins) on all other days during the inpatient stay (Days 3 to 8).

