8.11.7 Relationship Between Plasma Concentrations and Placebo-Corrected, Change from Baseline QTcF

The analyses described in this section may be conducted depending on the results observed. They will be based on the QT/QTc and PK/QTc Analysis Set.

QT/QTc Analysis Set will include all subjects in the Safety Set with measurements at baseline as well as on-treatment with at least one postdose timepoint with a valid Δ QTcF value. The QT/QTc Analysis Set will be used for the analysis of ECG parameters.

PK/QTc Analysis Set will include all subjects in both the QT/QTc and PK analysis sets with at least one pair of postdose PK and QTcF data from the same timepoint. The PK/QTc Analysis Set will be used for the exposure-response analysis.

Baseline: For all ECG parameters, baseline is defined as the measured QTc intervals from the time-matched predose timepoint on Day 1.

Exposure-Response Analysis

The relationship between NT-814 plasma concentration and Δ QTcF (change-from-baseline QTcF) will be quantified using a linear mixed-effects model with Δ QTcF as the dependent variable, NT-814 plasma concentration as a continuous covariate (zero for placebo), treatment (active or placebo) and time since drug administration as categorical factors, and a random intercept per subject. The degrees of freedom for the model estimates will be determined by the Kenward-Rogers method. From the model, the slope (i.e., the regression parameter for the concentration) and the treatment effect (defined as the difference between active and placebo) will be estimated together with 2-sided 90% CI. The estimates for the time effect will be reported with degrees of freedom and standard error (SE).

The geometric mean of the individual C_{\max} values for subjects in each of the NT-814 dose groups will be determined. The predicted effect and its 2-sided 90% CI for $\Delta\Delta$ QTcF (placebo-corrected change-from-baseline QTcF) (ie, the product with the slope estimate + treatment effect) at the geometric mean C_{\max} will be obtained for each NT-814 dose, separately. If the upper bound of the 90% confidence interval of the predicted effect at this plasma level is below 10 ms, it will be

concluded that NT-814 does not cause clinically relevant QTc prolongation. These analyses will be performed using the PK/QTc population.

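### The concentration-QTc model in SAP 8.11.7 lists no study-day factor, so if Days 1 and 14 are pooled and NT-814 accumulates, a day shift common to both arms biases the prediction behind the 10 ms conclusion

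*SAP*

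**What the plan says.** The exposure-response model in SAP 8.11.7 has change from baseline in QTcF as outcome and concentration as a continuous covariate (zero for placebo). Its other terms are "treatment (active or placebo) and time since drug administration as categorical factors, and a random intercept per subject". Neither study day nor a day interaction appears. The section does not say which days' data enter, or whether the time levels are shared across days.

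On the data available, SAP 4.10.5 states: "On Days 1 and 14, resting 12-lead ECG data will be collected at the following timepoints", followed by a predose and ten postdose times. SAP 4.9 states: "Blood samples for PK analysis will be collected at the following time points on Days 1, 7, and 14", and its times include all ten ECG times. Baseline in 8.11.7 is a Day 1 predose value, so both days are measured from one baseline.

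For each dose the predicted effect is "the product with the slope estimate + treatment effect", evaluated at a geometric mean Cmax. On that Cmax the text says only that "values for subjects in each of the NT-814 dose groups will be determined"; no day is named, although SAP 3.3 derives PK parameters on Days 1, 7 and 14. The decision rule begins: "If the upper bound of the 90% confidence interval of the predicted effect at this plasma level is below 10 ms". If it is met, NT-814 is declared free of clinically relevant QTc prolongation.

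On accumulation, Protocol 5.5 describes the first seven days of dosing as the time "when steady state plasma drug levels are predicted to be reached", and Protocol 11.3.3 says: "Accumulation and time invariance will be evaluated by comparisons of Day 1" exposure with Days 7 and 14. No half-life or accumulation ratio is given.

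**The concern.** In an active subject, accumulation makes concentration higher on Day 14 than on Day 1 at the same post-dose hour. In a placebo subject it is zero on both days. Suppose QTcF drifts by the same amount in everyone between the two days. The drift has nothing to do with the drug, but the listed model has no term for it: the hour effects are shared by both days, and treatment and the random intercept are constant over days within a subject. The only covariate that moves with day is concentration, so it picks up part of the drift. Pooled placebo subjects limit this but do not remove it.

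A common drift is plausible. On Day 1 subjects have already been resident since Day -1; on Day 14 they are re-admitted that morning after several days at home. Changing the baseline would not help, because any single baseline leaves a Day 14 minus Day 1 difference in the data.

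The stake is the 10 ms conclusion. A downward drift is the more worrying direction, since it could support a reassuring statement that the data do not justify.

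**Working it through.** The plan states no figure for this point, so there is none to reproduce. The bias was calculated directly.

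**Inputs from the documents.** 15 active subjects at each of 50, 100, 150 and 300 mg, and 4 × 5 = 20 on placebo (PK SAP Section 3); ten postdose ECG times on each of two days (SAP 4.10.5); log-scale SD 0.413, borrowed from the AUC figure in SAP 8.12 to spread exposures between subjects.

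**Assumptions not in the documents.** One-compartment oral PK; half-life 8 to 36 h; between/within-subject QTcF SD of 7/7 or 5/9 ms; no true drug effect; one shift δ on Day 14 common to all subjects.

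**Formula.** With X the design matrix of the SAP model, V the random-intercept covariance and d the Day 14 indicator, the expected coefficients are (XᵀV⁻¹X)⁻¹XᵀV⁻¹d·δ. Bias in the prediction = slope bias × Cmax + treatment-term bias. It is linear in δ, so results are given per 1 ms of shift, at the Day 14 Cmax.

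| Half-life (SD 7/7) | Day 14/Day 1 Cmax | Slope × Cmax, 300 mg | Treatment term | Net, 300 mg | Net, 50 mg |
|---|---|---|---|---|---|
| 8 h | 1.16 | 0.88 | -0.33 | 0.56 | -0.18 |
| 12 h | 1.38 | 1.68 | -0.65 | 1.03 | -0.35 |
| 24 h | 2.16 | 1.52 | -0.47 | 1.05 | -0.28 |
| 36 h | 2.81 | 1.76 | -0.58 | 1.19 | -0.30 |

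With SD 5/9 the net figures at 300 mg are 0.48, 0.88, 0.69 and 0.96. Each row is one simulated set of subjects, so the figures are good to a few tenths and are not smooth in half-life. A separate run at 18 h gave 1.23 to 1.25, and a half-life near 4 h gave about 0.03.

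**A 5 ms shift at 300 mg.** 5 × 0.03 = 0.15 ms at 4 h; 5 × 0.48 = 2.4 ms at the low end of the 8 h runs; 5 × 1.19 = 5.9 ms at 36 h; 5 × 1.23 = 6.2 ms at 18 h. The sign follows the shift. At 50 mg the largest figure is 5 × (-0.35) = about -1.7 ms.

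**Effect on the decision.** Take the 24 h row, where the 90% half-width is 3.25 ms, a true effect of 10 ms at 300 mg (linear in concentration), and a common shift of -5 ms. The expected prediction is 10 - 5.2 = 4.8 ms and the upper bound 4.8 + 3.25 = 8.05 ms, so the rule is met. Without the shift the upper bound is 13.25 ms and the rule fails.

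**With a day term.** The bias is 0.00 in every scenario. The half-width at 300 mg widens from 3.25 to 3.33 ms (24 h, SD 7/7), and at most from 2.59 to 2.74 ms, i.e. by 0.15 ms (36 h, SD 5/9).

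**What the documents hint about half-life.** Protocol 9.2 gives, for 200 mg daily, a geometric mean AUC0-24 of 14040 ng.h/mL and a predicted Cmax of 1836 ng/mL. The average concentration is 14040/24 = 585 ng/mL, so Cmax/average = 1836/585 = 3.1. One-compartment profiles that peaked need a half-life of about 3.6 to 4.7 h, with Day 14/Day 1 Cmax of 1.01 to 1.03 and net bias of 0.02 to 0.06 per ms. Two-compartment profiles tuned to the same ratio gave mostly 0.05 to 0.7 per ms, at the extreme about 1.0, with a Cmax ratio of at most about 1.26.

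**The case against.** The strongest reply is that the documents' own PK figures point to little accumulation. On a one-compartment reading, the peak-to-average ratio of 3.1 makes the bias negligible. This stands as a reason to start the range near zero. It does not close the matter: the AUC was observed in males after 28 days, the Cmax is a prediction for 14 days, and two-compartment profiles with the same ratio still give material bias.

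Second, the SAP does not say that the days are pooled with shared time levels. If each Day 1 and Day 14 timepoint has its own level, the problem disappears. That is correct. The post-dose-hour reading is the more natural one, because the section's plots are described as corrected for diurnal variation, but it is an inference.

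Third, the by-timepoint model in 8.11.7 compares each dose with placebo at each timepoint, so a common shift cancels if its timepoints are day-specific. The residual and Loess plots are a further check. However, neither feeds the 10 ms conclusion, and the plots do not target a day effect.

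Fourth, the analysis is conditional and exploratory, and Protocol 11 specifies no primary hypothesis test. This lowers the stakes. Still, if the analysis is run it yields a categorical safety statement, and safety is part of the primary objective.

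A reader might go further and infer that Day 14 concentrations are known to be higher, or that the whole of any day effect goes into the slope. The documents support neither: accumulation is expected but no value is given, and the treatment term takes back part of the bias, enough to reverse the net sign at 50 mg.

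**Conclusion.** The point holds conditionally. The listed model has no study-day factor. If Days 1 and 14 are pooled by post-dose hour and NT-814 accumulates, a QTcF shift common to both arms biases both the slope and the predicted effect used for the 10 ms rule. At the 300 mg Day 14 Cmax the net bias lies between near 0 and about 1.2 ms per 1 ms of shift, so a 5 ms shift moves the prediction by 0 to about 6 ms in either direction. The range reflects assumed PK and assumed QTcF variances, and the 5 ms is illustrative: no document gives or suggests a common shift of any size. A larger effect, say 7 ms or more from a 5 ms shift, is not supported by these results. With no accumulation there is essentially no bias.

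The unnamed Cmax day is a smaller, related gap. Under the assumed PK, Day 14 Cmax is between 1.01 and 2.8 times Day 1 Cmax, so the concentration at which the rule is tested is left open to the same degree.

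This is worth correcting before the model is run, because the remedy is cheap and does not depend on which PK assumption is right.

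**What to change.** In SAP 8.11.7:

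- State that Day 1 and Day 14 data enter the exposure-response model.
- Replace time since drug administration with study day, time and day-by-time as categorical factors, so that each Day 1 and Day 14 timepoint has its own level.
- State that the prediction for each dose uses the higher of the Day 1 and Day 14 geometric mean Cmax.
- State that placebo subjects are in the exposure-response data set with concentration zero. As written, the PK/QTc set requires membership of the PK set, and PK SAP Section 7 excludes placebo from that set. Taken literally, the treatment effect could not be estimated and, without a day term, the bias at 300 mg would be 0.9 to 2.0 ms per ms over the 8 to 36 h runs.

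Cost: SAP wording and 20 - 10 = 10 more fixed-effect parameters, against roughly 80 × 20 = 1600 records. A single day term widened the 90% half-width at 300 mg by up to about 0.15 ms; a check with the full day-by-time factor gave nearly the same widths as the single term.

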The plot of the observed median-quantile NT-814 concentrations and associated mean $\Delta\Delta\text{QTcF}$ (90% CI) adjusted for diurnal effects together with the regression line presenting the predicted $\Delta\Delta\text{QTcF}$ (90% CI) (as described in the publication by Tornoe et al¹) will be used to evaluate the adequacy of the model fit to the assumption of linearity and the impact on quantifying the exposure response relationship. Additional exploratory analyses (via graphical displays and/or model fitting) will include accounting for a delayed effect (hysteresis) and the justification for the choice of pharmacodynamic model (linear versus nonlinear) as follows.

Investigation of hysteresis

If a QTc effect ($\Delta\Delta\text{QTcF}$) exceeding 10 msec cannot be excluded in the by-timepoint analysis, hysteresis, i.e., difference in peak QT response and C_{max} , will be explored through visual inspection of overlaid NT-814 concentration and $\Delta\Delta\text{QTc}$ time curves and through so called hysteresis loops for each dose of NT-814.

Appropriateness of a linear model

To assess the appropriateness of a linear model, normal QQ-plots for the residuals and plots of weighted residuals versus concentration and vs. fitted values will be produced. The scatter plot of residuals versus concentration by Loess (i.e., locally weighted scatterplot smoothing as described in the publication by Cleveland²) fitting will be also produced with an optimal smoothing parameter selected by the Akaike information criterion with a correction (AICC³). In addition, a model with a quadratic term in concentration will be fitted and the quadratic term will be tested on the two-sided 5 % level. If there is an indication that a linear model is inappropriate, additional models will be fitted, in particular:

- An E-max model;
- A log-linear model where the plasma concentration (C) is replaced by $\log(C/C_0)$, C_0 is the limit of quantification of the assay used to determine C and all values below C_0 are replaced by C_0 (i.e., $\log[C_0/C_0] = 0$).

The Exposure-Response analysis will then be repeated for the model found to best accommodate the nonlinearity detected.

By-Timepoint Analysis:

¹ Tornoe C et al. J Clin Pharmacol 2011; 7: 1035-42

² Cleveland WS. J Amer Statist Assoc 1979; 74: 829-36

³ Hurvich, CM, Simonoff, JS, and Tsai, CL 1998; J. Roy. Statist. Soc. Ser. B, 60: 271-93.

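### SAP 8.11.7 has no rule linking a hysteresis finding to its 10 ms QTc conclusion, so a delayed effect near 10–15 ms can be cleared with probability well above 5%

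*SAP*

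**What the plan says.** The exposure-response model in SAP 8.11.7 has change from baseline in QTcF as outcome and a subject-level random intercept. Its other terms are "NT-814 plasma concentration as a continuous covariate (zero for placebo), treatment (active or placebo) and time since drug administration as categorical factors". QTcF is tied to the concentration at the same time, with no delay term. The placebo-corrected prediction (slope times concentration, plus treatment effect) "at the geometric mean C_{\max} will be obtained for each NT-814 dose, separately". The test is whether the upper 90% bound of this prediction lies under 10 ms. Where it does, the SAP would have it "concluded that NT-814 does not cause clinically relevant QTc prolongation". No further condition is attached.

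Model adequacy comes next. The lead-in says: "Additional exploratory analyses (via graphical displays and/or model fitting) will include accounting for a delayed effect (hysteresis". The hysteresis paragraph then gives the detail. When an effect "exceeding 10 msec cannot be excluded in the by-timepoint analysis, hysteresis" is to be looked at, and the stated method is that it "will be explored through visual inspection of overlaid NT-814 concentration and" QTc curves over time, together with hysteresis loops by dose. No criterion for a positive finding, no delay model and no consequence are given.

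Nonlinearity is treated differently. There is a quadratic test at 5%, residual and Loess plots, two named alternative models and a consequence: "The Exposure-Response analysis will then be repeated for the model found to best accommodate the nonlinearity detected".

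The by-timepoint analysis in the same section gives placebo-corrected estimates with 90% CIs for every dose and time. It triggers the hysteresis plots but is not an input to the 10 ms conclusion.

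**The concern.** The rule tests whether the no-delay model's value at Cmax is below 10 ms. That is the same as testing the peak effect only if QTcF follows plasma concentration without lag. The SAP describes hysteresis as a difference between the peak QT response and Cmax, which is exactly the case where the two questions part.

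With a lag, concentration is high while the effect is still small, and the effect is large when concentration has already fallen. The fitted slope is flattened and the prediction at Cmax falls below the true peak. Followed as written, the plan can report by-timepoint bounds above 10 ms and a clear hysteresis loop, and still state that there is no clinically relevant prolongation. This is the one numerical threshold on which the SAP bases a safety conclusion.

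**Working it through.** The documents state no error rate, power or QTc SD for this rule, so there is no figure of the plan's own to reproduce. The operating characteristics were simulated.

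**Inputs from the documents**
- Two-sided 90% CI, margin 10 ms, so nominally 5% one-sided (SAP 8.11.7).
- Ten post-dose ECG times on each of Days 1 and 14, all of them also PK times (SAP 4.10.5 and 4.9).
- 15 active and 5 placebo per cohort (SAP 4.1); cohorts of 50, 100, 150 and 300 mg (PK SAP section 3), so 4 × 5 = 20 pooled placebo.
- Log-scale SD 0.413, stated for AUC0-24 (SAP 8.12).
- At 200 mg, Cmax 1836 ng/mL and AUC0-24 14040 ng·h/mL (Protocol 9.2): 1836 / 14040 = 0.131 per h.

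**Assumptions not in the documents**
- One-compartment PK, ka 1.5/h and k 0.169/h, chosen to match 0.131 per h; Tmax about 1.65 h.
- QTcF SD 8 ms within and 6 ms between subjects.
- Effect linear in an effect-compartment concentration with rate ke0, scaled to the stated peak at 300 mg on Day 14. Equilibration half-life is ln 2 / ke0: 1.4, 2.8 and 6.9 h for ke0 of 0.5, 0.25 and 0.1/h.

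**Chance of concluding no prolongation (SAP model, 800 trials per scenario)**

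| Effect peak after Tmax | True peak 10 ms | 12 ms | 15 ms | Mean prediction at Cmax, true peak 10 ms |
|---|---|---|---|---|
| no delay | 8% | 1% | 0% | – |
| 2.4 h | 56% | 31% | 5% | 6.8 ms |
| 3.8 h | 88% | 73% | 46% | 4.8 ms |
| 5.6 h | 98% | 96% | 87% | 3.2 ms |

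**Check by formula.** The rule passes when prediction + 1.645 SE < 10, so P(pass) ≈ Φ((10 − mean prediction)/SE − 1.645). The 88% cell gives (10 − 4.8)/SE ≈ 1.16 + 1.645 = 2.80, so SE is about 1.8 ms by this approximation. With SE 1.8:
- 6.8 ms: Φ(3.2/1.8 − 1.645) = Φ(0.13) = 55%
- 4.8 ms: Φ(5.2/1.8 − 1.645) = Φ(1.24) = 89%
- 3.2 ms: Φ(6.8/1.8 − 1.645) = Φ(2.13) = 98%

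Scaling 4.8 ms by 1.5 for a 15 ms peak gives 7.2 ms and Φ(2.8/1.8 − 1.645) = Φ(−0.09) = 46%, as simulated. The excess over 5% is therefore explained by bias in the Cmax prediction.

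**Sensitivity.** The same design was run with two other PK shapes matched to the protocol's Cmax and AUC, and with QTcF SDs of 8/6 or 5/5 ms (200–300 trials per cell):

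| Equilibration half-life (time of QTc peak) | 10 ms | 12 ms | 15 ms | 20 ms |
|---|---|---|---|---|
| none | 8–11% | 2% | 0% | – |
| 1 h (about 3–3.5 h) | 32–54% | 12–19% | 2% | – |
| 2 h (about 4–5 h) | 63–88% | 40–66% | 12–26% | 1–2% |
| 4 h (about 5–6 h) | 88–99% | 73–98% | 45–86% | 10–40% |
| 8 h (about 6–7.5 h) | 93–100% | 86–99% | 63–98% | 23–76% |

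A flatter profile (12 h half-life, which does not match the protocol's ratio), with delays of 1–8 h, gives 23–60% at 10 ms, 6–25% at 12 ms and 0–3% at 15 ms. Five cohorts up to 400 mg, or day-by-time categories, change little.

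**Do the other checks intervene?** In the delayed 10 ms trials of the first table, the quadratic term was significant in 12–27%, and 49–83% of trials were cleared with it non-significant. The by-timepoint trigger fired in 99–100% of delayed trials, so the plots would be made but would change nothing.

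**The case against.** Several points on the other side have force.

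- A reader might infer that any delayed effect of 10 ms or more would usually be cleared. The calculations do not support that: 15 ms with a 2.4 h lag is cleared in 5%, and 20 ms with a 2 h equilibration half-life in 1–2%.
- A reader might also infer that the SAP rules out anything beyond inspection by eye. It does not, because the lead-in allows model fitting to account for a delayed effect. But the hysteresis detail is graphical only, and nothing ties a delay model to the 10 ms rule.
- The signal would not be hidden. By-timepoint estimates, their CIs and the outlier tables are all reported. What is missing is a statement of which result governs when they disagree with the Cmax prediction.
- A 4.1 h half-life (ln 2 / 0.169) sits poorly with the 48 and 72 h samples in Protocol 10.3. With assumed terminal half-lives of 10–24 h and the same Cmax/AUC ratio, clearance at ke0 0.25/h is 72–84% for 10 ms and 22–38% for 15 ms. At ke0 0.1/h and 15 ms it is 42–74%. The direction holds; the upper figures depend on the model.
- Only the quadratic term was simulated among the linearity checks. The Loess and residual plots might prompt other models, though the two named ones use the concurrent concentration.
- The section is exploratory and may not be run at all, and Protocol 11 pre-specifies no primary hypothesis test. That lowers the stakes. If the section is run, the rule applies as written.

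**Conclusion.** The point holds as a missing link between two parts of SAP 8.11.7. The no-prolongation conclusion is unconditional, rests on a no-delay prediction at Cmax, and is not changed by a finding of hysteresis.

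If QTcF lags concentration, a true peak near 10–15 ms can be cleared with probability well above the nominal 5%. At 10–12 ms this is often above 50% when the effect peaks several hours after Tmax. It is much lower for short delays (2% at 15 ms with a 1 h equilibration half-life) and, except with the longest delays, for effects of 20 ms.

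The delay, QTc SDs and PK shape are assumed, and the documents give no evidence for or against a delay. The point is therefore about what the rule would do under a delay, not a prediction that NT-814 has one. It should be corrected before the analysis is run, so that the response to a delay is not chosen after seeing the data.

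**What to change.** Make the conclusion sentence in SAP 8.11.7 conditional on the hysteresis assessment, and add a rule to the hysteresis paragraph along these lines:

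- **Trigger.** The by-timepoint analysis cannot exclude 10 ms, and hysteresis meets a pre-specified criterion. For example: the peak mean placebo-corrected QTcF lags the mean concentration peak consistently across the higher doses and on both Day 1 and Day 14, with a mean effect above a stated minimum size.
- **Action.** Repeat the exposure-response analysis with a delayed-effect model and apply the 10 ms criterion to the peak effect it predicts.
- **Fallback.** If no adequate delayed model can be fitted, do not draw the no-prolongation conclusion from the Cmax prediction, and report the by-timepoint estimates with 90% CIs.

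The consistency and minimum-size conditions matter. With no QTc effect at all (SDs 8/6 ms, one day, top dose), noise alone put the observed peak after 2 h in about 59% of simulated trials, and in about 28% with the by-timepoint trigger also met.

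The cost is a few sentences, one extra model fit on data already scheduled, and a conclusion that may sometimes be withheld. In a best case, refitting on the true effect-site concentration brought clearance at 10 ms back to 6.5–7.7%; an estimated delay would do less well, and the proposed trigger itself was not simulated. Simply requiring every top-dose by-timepoint bound to be below 10 ms is cruder. It cuts wrong clearance to about 0–1%, but clears a drug with no QTc effect in only 37% of trials (SDs 8/6) or 92% (5/5), against 100% under the present rule.
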